2.1. Plain language summary

One of the commonest sources of serious newborn morbidity and mortality is difficulty with breathing. When this occurs, three main types of supportive therapy are available to increase the provision of oxygen to cells: a) passive provision of oxygen-enriched gases (i.e., higher than the 21% O₂ found in the earth's atmosphere) through tubes in the nostrils, or by putting a hood over the baby's head and enriching the gases under that hood; b) provision of room air or oxygen-enriched gasses under pressure, frequently performed using a method called continuous positive airway pressure [CPAP] therapy; and/or c) by using a machine that is able to breath on behalf of the baby, most commonly referred to as mechanical ventilation [MV].

Passive therapy is the least invasive method but is also of limited benefit, particularly for infants born preterm. CPAP is more effective than passive methods because continuous distending pressure to the lungs allows better oxygen exchange; however, the distending pressure increases the risk of damage to the lung. MV is the only method that can be used on babies without a neurological impulse to breath, but the mechanical breathing action can damage the lungs, and MV is usually provided through a tube inserted into the lungs which increases the risk of lung infection; MV machines are also significantly more expensive than CPAP machines.

In high resource settings, CPAP is now the preferred method of providing oxygen for infants where passive therapy is insufficient, because of the lower infection risk, lower risk of lung damage, and relative ease of clinical care. CPAP is increasingly recommended for low resource settings, but the CPAP machines used in high resource settings are too expensive for low resource settings due to high-priced consumables (\$US50-200/baby), and are usually unusable in low resource settings because they require 'medical air' (clean air in a cylinder, or through a piped wall system) with which to blend 100% oxygen. Low cost 'indigenous' machines ('jury-rigged' by hospital staff) have also been developed, but these do not provide the heated, humidified and blended gasses, that are recommended for CPAP.

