- d) Infants clinically suspected to have another specified serious condition as their main disease process, ***diagnosed prior to randomisation***, specifically: cardiac anomaly, other congenital malformation with respiratory sequelae, septicaemia, pulmonary haemorrhage, pneumothorax, meningitis, poor respiratory effort or recurrent apnoea, or brain haemorrhage (IVH Grades III or IV);
- e) Infants who have an airway abnormality precluding the use of the standard CPAP interface proposed for this study (e.g., Pierre-Robin sequence, cleft lip or cleft palate) or who have a neuromuscular condition that interferes with respiration;
- f) Any infant whose treating clinician believes should not be randomised due to some other condition, or for any other reason (reason to be documented).

3.2. ***Primary outcome***

The primary outcome will be a comparison of fraction of inspired oxygen (FiO₂), measured as a change from baseline at 6, 12, 24, 48 and 72 hours after treatment commencement.

3.3. ***Secondary outcomes***

A range of secondary outcomes will be assessed:

- Oxygen saturation by pulse oximetry (SpO₂), measured as a change from baseline at 6, 12, 24, 48 and 72 hours after treatment commencement;
- Respiratory rate (breaths/minute), measured as a change from baseline at 6, 12, 24, 48 and 72 hours after treatment commencement;
- Arterial blood gas analyses, measured as a change from baseline at 6, 12, 24, 48 and 72 hours after treatment commencement, including:
 - pH;
 - Partial pressure of oxygen (PaO₂); and
 - Partial pressure of carbon dioxide (PaCO₂).
- CPAP failure (death or need for intubation and mechanical ventilation as demonstrated by an FiO₂ requirement $\geq 60\%$ for ≥ 1 hour to maintain SpO₂ at 90-95%);

- Surfactant provided when $\text{FiO}_2 > 40\%$ to maintain SpO_2 at 90-95% for ≥ 30 minutes, with RDS confirmed by chest X-Ray, in line with current Ramaiah standard practice;
- An omnibus indicator comprising CPAP failure or surfactant provision;
- Duration of CPAP treatment (hours) in infants that do not fail CPAP;
- Selected complications of treatment will be evaluated as sentinel outcomes. These, include:
 - Damage to the nasal septum;
 - Damage to the nares;
 - Pneumothorax as diagnosed by X-ray;
 - Intra-ventricular haemorrhage (IVH), intra-cranial haemorrhage (ICH), or periventricular leukomalacia (PVL) as diagnosed by cranial ultrasound scan;

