4.5. Measurement of outcomes

As blinding to exposure is not possible, it is important that steps are taken to prevent differential measurement error. Thus, the following steps will be taken to ensure consistency of measurement in the two treatment arms:

Primary outcome:

FiO₂ is measured on the CPAP machines themselves, which creates a possibility of differential error. The oxygen readings for the study will be algorithmically or arithmetically calibrated prior to analysis, based on measurement of FiO₂ as the gas exits the patient interface, to identify if there are any systematic differences in the reported FiO₂ being provided and the actual FiO₂ delivered to the patient interface; this will be done prior to study commencement and at the end of the first, third, fifth and seventh months after commencement. The AAI model PSR-11-917-MH oxygen analyser will measure the FiO₂ delivered against that reported by each CPAP machine across the full range of FiO₂ (21%, 25%, 30%, 35%, and every 10% from 40%-99%).

Secondary outcomes:

- SpO₂: SpO₂ will be measured using the same stand-alone pulse oximeters in both the intervention and control arms (i.e., ignoring the built-in pulse oximeter on the new CPAP to prevent differential measurement error) – both groups will be monitored using the Mindray multichannel monitor (MEC 3000), placed on the right hand/arm (i.e., pre-ductal) in line with a standardised SpO₂ measurement protocol developed for the study, which will apply to both treatment groups;
- Respiratory rate: A standard measurement protocol will be developed and introduced which requires measurement of respiratory rate over 30 seconds at 0, 6, 24, 48 and 72 hours, doubling this number to achieve a rate per minute. The protocol will outline the conditions under which measurement is to take place, and the extent to which measurement can be deferred if an infant has a temporarily elevated respiratory rate due, for example, to crying;
- Arterial blood gases: A standard measurement protocol will be introduced which governs the process for taking arterial blood samples at 0, 6, 24, 48 and 72 hours. If blood samples

are not required for clinical management, they will be ceased, so not all readings will be performed for all babies.

- Damage to septum: A standard measurement protocol will be introduced which governs the process for diagnosing damaged septum;

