Primary outcome: With longitudinal measurement, the interpretation of later results can be impacted by differential losses before 72 hours (death or intubation and ventilation). Analysis will therefore commence with a Kaplan-Meier curve comparing 'loss' (death or intubation and ventilation), and an associated Cox regression model to compare the rate of loss in the two treatment arms. The results of this survival analysis will provide the context within which the longitudinal results will be interpreted. If there are differential losses over time, the least affected time point will be 6 hours after treatment commencement, and this time point will be promoted to being the primary outcome. If losses over time are not differential, the planned analysis is described below.

The preferred omnibus analysis is a longitudinal mixed effects model (using PROC MIXED in SAS 9.4), controlling for baseline through a random 'intercept', in line with international recommendations for controls on baseline.^[30] Individual analyses at each time point (6, 12, 24, 48, and 72 hours) will be by multiple regression, again adjusting for baseline as a covariate.^[30] If multiple regression model requirements for normality and homoscedasticity are not met, analysis will be by t-test which is known to be robust to violations of the normality assumption, and will be based on the change in variable from baseline value, providing some control for different baselines, but without the additional control offered by multivariate analysis.

Where performed, multivariate analysis will control for stratification; if univariate analysis is used, separate stratum-specific sub-analysis will be undertaken, and a stratified t-test will be performed. Additional covariates will be adjusted for in multivariate analysis, if the baseline comparison shows substantial group difference in significant prognostic factors (e.g., onset of labour is associated with the stimulation of surfactant production, so analysis will control for mode of delivery if there is a clinically relevant mal-distribution).

Secondary outcomes: Five of the secondary outcomes (SpO_2 , respiratory rate, pH, PaO_2 , PaCO_2) will be analysed using the same procedures as for the primary outcome. It is anticipated that the three arterial blood gases (pH, PaO_2 , PaCO_2) will not be performed on all infants, particularly infants that recover rapidly; if so, this analysis will be restricted to change from baseline at the 6-hour reading.

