- Kaplan-Meier curve produced to assess treatment failure in the first 72 hours, with difference assessed by log-rank test. Three Dolphin and one Fisher-Paykel failure in first 72 hours; not statistically different by log-rank test, $p=0.30$. Two infants ceased CPAP and were discharged <72 hours (one left against medical advice, the other discharged home), and were excluded from the denominators from the point of discharge. No control for stratification in analysis, as no failures in the older gestational group.

Statistical Analysis Plan

“Randomised trial comparing CPAP machines with reusable vs disposable circuits”

- c. While the difference between groups was not statistically significant in survival analysis, change at in FiO₂ from baseline to 6 hours was preferred as the primary endpoint, given the small sample size. As the distribution was strongly peaked, a non-distributional test (Wilcoxon) was preferred, controlling for stratification (van Elteren's extension).

Secondary outcomes

7. Descriptive analysis as specified in the protocol:

Primary and selected secondary outcomes - descriptive: The raw values of the primary outcome (FiO₂) and five secondary outcomes (SpO₂, respiratory rate, pH, PaO₂, PaCO₂) will be graphed to allow visual comparison of differences at baseline and over time. [Protocol, para 5.2]

8. Descriptive analysis as revised: No change.

9. Analyses as specified in the protocol:

Secondary outcomes: Five of the secondary outcomes (SpO₂, respiratory rate, pH, PaO₂, PaCO₂) will be analysed using the same procedures as for the primary outcome. It is anticipated that the three arterial blood gases (pH, PaO₂, PaCO₂) will not be performed on all infants, particularly infants that recover rapidly; if so, this analysis will be restricted to change from baseline at the 6-hour reading.

Duration of CPAP (hours), for those not failing CPAP treatment, is the only continuous secondary outcome this is expected to be non-normally distributed and will therefore be assessed using Wilcoxon's rank sum test, with stratum-specific contributions aggregated using van Elteren's extension to the Wilcoxon test.^[31]

The remaining secondary outcomes are dichotomous and will be tabulated and compared using stratum-specific relative risks (RRs); the homogeneity of stratum-specific RRs will be assessed using Cochran's Q and the I² tests^[32]. [Protocol, para 5.2]

10. Revisions to planned analysis:

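### SAP para 6c tests raw 6-hour change in FiO2 without the protocol's baseline adjustment, so infants in room air at 6 hours are ranked among themselves only by their pre-CPAP oxygen

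*SAP*

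**What the plan says.** Protocol 3.2 defines the primary outcome as FiO2 "measured as a change from baseline at 6, 12, 24, 48 and 72 hours after treatment commencement". Change from baseline is therefore the protocol's own variable.

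For single time points, Protocol 5.2 says the analysis "will be by multiple regression, again adjusting for baseline as a covariate". If normality and homoscedasticity fail, the fallback is a t-test "based on the change in variable from baseline value, providing some control for different baselines". The same sentence concedes that this gives up the extra control of a multivariable model.

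The SAP repeats that text in para 5 and revises it in para 6c. There, change in FiO2 "from baseline to 6 hours was preferred as the primary endpoint, given the small sample size", and the test changes: "As the distribution was strongly peaked, a non-distributional test (Wilcoxon) was preferred, controlling for stratification". The stratification is by gestational age group. No baseline FiO2 covariate remains.

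Protocol 4.5 has the oxygen analyser check each machine "across the full range of FiO₂ (21%, 25%, 30%, 35%, and every 10% from 40%-99" percent, so the range starts at 21%. Protocol 2.1 describes CPAP as "provision of room air or oxygen-enriched gasses under pressure, frequently performed using a method called continuous positive airway pressure", so CPAP without added oxygen is possible. Annex B, item 3d, places the baseline reading immediately before CPAP starts. Neither document discusses the 21% floor.

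**The concern.** A change score works as a measure of response when the later value is free to move. At a floor it is not. Two infants who both need no added oxygen at 6 hours have reached the same state, yet the one who started higher gets the better score. That difference was fixed before either machine was attached. Van Elteren's test does not correct this, because it compares ranks of change within gestational strata and never uses baseline FiO2.

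The trial has little power to spare. SAP para 2a accepts that 51 infants instead of 80 cuts power substantially, and SAP para 11 reads any significant secondary result in the light of the primary one. If many infants were at 21% by 6 hours, a real difference in oxygen need could be diluted and a null result taken to mean that the machines perform alike.

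**Working it through.** **The plan's own figure.** With 40 per arm, 80% power and two-sided 5% alpha, the detectable difference is (1.960 + 0.842) × √(2/40) = 2.802 × 0.2236 = 0.627 SD. This reproduces the 0.63 SD in Protocol 5.1. With 51 infants, split 26/25 by assumption, it is 2.802 × √(1/25 + 1/26) = 2.802 × 0.2801 = 0.785 SD, or 0.80 SD using the t distribution. Power for 0.63 SD falls to about 60% before any floor effect.

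**The score at the floor.** Change = FiO2 at 6 hours − baseline.
- 30% to 21%: 21 − 30 = −9.
- 50% to 21%: 21 − 50 = −29, a much better rank for the same end state.
- 60% to 40%: 40 − 60 = −20. This infant is still on oxygen but ranks as a larger fall than the infant who went from 30% to room air.

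**Simulation 1.** Assumed, because the documents give no FiO2 distribution: 51 infants, two strata, baseline mean 40% and SD 10 points, correlation of baseline with 6-hour FiO2 0.6, true arm difference 6.3 points (0.63 SD), floor at 21%, 1,500 runs per cell. The adjusted test takes residuals of 6-hour ranks on baseline ranks and stratum, then applies van Elteren's test.

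| Share at 21% at 6 h (no arm effect) | Spearman correlation, change with baseline | Power, change score | Power, baseline-adjusted ranks |
|---|---|---|---|
| 1% | −0.41 | 65% | 71% |
| 20% | −0.55 | 59% | 69% |
| 52% | −0.80 | 34% | 63% |
| 77% | −0.93 | 14% | 47% |
| 91% | −0.98 | 6% | 23% |

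With no arm effect the change-score test rejected in 4.3% to 6.4% of runs, so its type I error holds. One named arm had a chance baseline excess above 0.3 SD in 13% to 16% of runs. In those runs the change-score test rejected in 9% to 21%, against 3% to 11% for the adjusted test.

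**Simulation 2.** True difference 8 points, 5-point dial steps, other assumptions as above. Power, change score against adjusted ranks:
- Correlation 0.6: 77% v 87% with 14% at the floor; 63% v 84% with 28%; 41% v 81% with 45%.
- Correlation 0.3: 56% v 77% with 15%; 45% v 72% with 27%; 30% v 69% with 45%.
- Correlation 0.3 and no floor: about 60% v 76%. Much of the gap at low correlation is therefore ordinary change-score inefficiency.
- Correlation 0.8 with 11% at the floor: 98% v 97%.

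**Simulation 3.** Heavy-tailed change (excess kurtosis about 4 to 5), 6-hour FiO2 following baseline one for one, baseline centre 30%, 5-point difference:
- Narrow baseline spread: 91% v 88% with 16% at the floor; 86% v 86% with 27%; 78% v 86% with 38%.
- Wider baseline spread: 89% v 80% with 23%; 79% v 81% with 34%; 63% v 77% with 42%.

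Here the SAP's test matches or beats the adjusted one until roughly a third of infants are at 21%.

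**The case against.** The strongest reply is that no passage says that any infant was at 21% by 6 hours. The room-air remark in Protocol 2.1 is general background, and the step-down rules sit in a separate clinical protocol (Protocol 6.2). This stands. SAP para 10b reports no infant with sustained FiO2 of 60% or more, and the SpO2 readings in SAP para 2b fall from 51 at baseline to 9 at 72 hours. Both fit quick recovery, but neither gives a share at 21%.

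The SAP's one distributional remark, that the distribution was strongly peaked, also fits the heavy-tailed model better than the normal one, whose change scores are not peaked. This stands too, and it is why the low end of the range is no loss. Nor does the peak show a pile-up at the floor: many infants at 21% with widely spread baselines would spread the change scores out.

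A reader might infer that the test ranks all infants by starting oxygen and not by the machine. The documents do not support that. The ordering by baseline is exact only among infants at the floor, and reaching the floor is itself a response. A reader might also infer a biased test. Randomisation balances baseline in expectation, and type I error stays near 5%. Nor did the SAP introduce change from baseline; what it removed was the covariate.

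Finally, the SAP already discloses low power and difficulty in interpreting FiO2 when SpO2 is above target (para 2), describes the study as exploratory (para 11) and graphs raw FiO2 (paras 3 and 4). This softens the point, but none of it mentions the floor or restores the adjustment. Because the SAP was updated in August 2019, after recruitment ended, replacing the lead analysis again would be one more post hoc switch. That is a good reason to add an analysis and not to substitute one.

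**Conclusion.** The point holds as a cheap improvement, not as a flaw that invalidates the primary test. Certain from the documents: the 21% lower bound, a baseline taken before CPAP, the missing baseline covariate in SAP para 6c, and hence a score of 21 minus baseline for any infant in room air at 6 hours. Calibration of the readings (Protocol 4.5) could shift the analysed floor slightly without changing the argument.

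Uncertain is the size. On assumed distributions the loss is nil with few infants at the floor and baseline closely tracked, or with peaked change up to about a third at the floor. It reaches about half the power at about 45% (41/81 = 0.51), and more beyond that. The count of infants at 21% would narrow this range considerably.

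**What to change.** In SAP para 6c, add a named stratified rank ANCOVA of 6-hour FiO2: rank 6-hour and baseline FiO2 within each gestational stratum, take residuals of the 6-hour ranks on the baseline ranks, and apply van Elteren's test to the residuals. This keeps the SAP's rank approach and restores the adjustment in Protocol 5.2. Report it beside the change-score test, show both results whatever they are, and label the adjusted one as added after data collection.

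Report, by arm, the number of infants at 21% at baseline and at 6 hours. State that a null change-score result will not be read as equivalence if many infants are at 21%.

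The cost is a few lines of SAP text, one more analysis step on data already collected, and a second result to present and explain.

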Randomised trial comparing CPAP machines with reusable vs disposable circuits

STEERING COMMITTEE

Primary Investigator:

[name] [name], MS Ramaiah Medical College

Co-investigators:

[name] M, MS Ramaiah Medical College

[name] MV, MS Ramaiah Medical College

Other Guidance:

The Wellcome Trust Research Steering Group provided assistance and guidance with protocol design.

Members providing technical input included:

[name], Neonatologist, in the role of Consultant to the Wellcome Trust

[name], Consultant to MTTS

PARTICIPATING SITES

M.S. Ramaiah Medical College, Bangalore, Karnataka, India.

TRIAL CONTACT

[name] [name]

MS Ramaiah Medical College

Email: [contact]

[contact]

INSTITUTIONAL ETHICS COMMITTEE

[name] (Chairman)

Ethics Committee

M S Ramaiah Medical College and Hospitals

[name]

[name]

Email: [contact]; [contact]

[contact]

TRIAL SUMMARY

1. Aim & Hypothesis:

The study aims to assess the basic functionality of a newly designed CPAP machine with reusable circuits to existing machines with disposable circuits, for treatment of newborn infants diagnosed with respiratory distress syndrome. The assessment will compare a comprehensive list of physiological parameters over the first 72 hours of treatment, and will also monitor rates of side effects and adverse events. The null hypothesis is that infants treated on the two categories of machine (reusable vs disposable) will not differ in relation to key physiological parameters by more than 0.63 standard deviations.

2. **Background:**

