- a. As with the primary endpoint, change from baseline at the 6-hour reading was adopted as the preferred analysis for SpO₂ (Secondary outcome #2), respiratory rate (Secondary outcome #3), pH, PaO₂, PaCO₂ (all reported as part of Secondary outcome #4) and duration of CPAP (Secondary outcome #8). Due to concerns about non-normality, van Elteren's extension to the Wilcoxon test was used to assess statistical significance, while controlling for stratification by gestational age group. No testing was performed for Secondary outcome #4 (pH, PaO₂, PaCO₂) as there were only five infants who had readings at both baseline and six hours of age.
- b. Dichotomous secondary outcomes were compared using the Cochran-Mantel-Haenszel test, with assessment for homogeneity using the Breslow-Day test. The exceptions to this were:
 - Where there were no events in one stratum (i.e., CPAP failure [Secondary outcome #5], Serious Adverse Event [Secondary outcome #9], Intubation and mechanical ventilation [Secondary outcome #15] and Death [Secondary outcome #17]), Fisher's Exact test was used on the full data; and
 - Where there were no events in either stratum (Damage to the nasal septum [Secondary outcome #10], Damage to the nares [Secondary outcome #11], Pneumothorax

Statistical Analysis Plan

“Randomised trial comparing CPAP machines with reusable vs disposable circuits”

diagnosed by X-Ray [Secondary outcome #12], Intra-ventricular haemorrhage (IVH), intra-cranial haemorrhage (ICH), or periventricular leukomalacia (PVL) as diagnosed by cranial ultrasound scan [Secondary outcome #13], $\text{FiO}_2 \geq 60\%$ to maintain SpO_2 at 90-95% for one hour or more, during CPAP treatment [Secondary outcome #14] and, for infants born at 28+0 to 33+6 weeks' gestation, oxygen dependent at 36 weeks' gestation [Secondary outcome #16]), no statistical test was performed.

Other issues

11. **Multiple comparisons:** The principal control for multiple comparisons was the designation of a single primary endpoint.

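### SAP 6c (and 10a for SpO2 and respiratory rate) names only a van Elteren test at 6 hours; report the protocol's baseline-adjusted difference with a 95% CI beside it

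*SAP*

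**What the plan says.** **Protocol 3.2** defines the primary outcome as FiO2 "measured as a change from baseline at 6, 12, 24, 48 and 72 hours after treatment commencement". **Protocol 5.2** makes a longitudinal mixed model the preferred omnibus analysis. Analysis at each individual time point "will be by multiple regression, again adjusting for baseline as a covariate", with control for the gestational stratum. It then gives a fallback: "If multiple regression model requirements for normality and homoscedasticity are not met, analysis will be by t-test which is known to be robust". The fallback works on change from baseline and is acknowledged to be "without the additional control offered by multivariate analysis". In that case "separate stratum-specific sub-analysis will be undertaken, and a stratified t-test will be performed".

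**Protocol 1** words the null hypothesis as infants on the two types of machine who "will not differ in relation to key physiological parameters by more than 0.63 standard deviations".

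**SAP 6c** takes the change in FiO2 from baseline to 6 hours as the primary endpoint because the sample was small, and names the test: "As the distribution was strongly peaked, a non-distributional test (Wilcoxon) was preferred, controlling for stratification". **SAP 10a** adopts the 6-hour change for SpO2 and respiratory rate and cites concerns about non-normality. There, van Elteren's "extension to the Wilcoxon test was used to assess statistical significance, while controlling for stratification by gestational age group".

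Apart from graphs of raw values (SAP 4 and 8), the SAP names nothing else for these outcomes. Neither document mentions a confidence interval.

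**The concern.** Both of the protocol's analyses at a single time point estimate a mean difference between arms. The SAP replaces them with a significance test and names no estimate. The SAP was updated on 31 August 2019, after the trial ended in July 2018, and it already reports results, so the test was chosen with the data in view.

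Two things are at stake. First, the trial's hypothesis concerns the size of a difference, and 51 infants were recruited instead of 80. A non-significant p-value from that sample could be read as showing that the machines perform alike, which it cannot show. Second, a reader cannot see whether the 6-hour conclusion depends on the choice of test unless the analysis that the protocol planned for that time point is shown beside it.

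**Working it through.** **Inputs from the documents.** 40 per arm planned, 80% power, 5% false-positive rate, 0.63 SD (Protocol 5.1); 51 infants achieved (SAP 2a); 50 SpO2 readings at 6 hours (SAP 2b).

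**Assumptions.** Two-sided test; 25 per arm at 6 hours, with the SpO2 count taken to apply to FiO2; strata of 30 and 20; equal SDs at baseline and 6 hours. The baseline to 6-hour correlation (rho) is not given, so a range is shown.

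**1. The plan's own figure.** With the t distribution, 40 per arm detects 0.634 SD at 80% power, which reproduces 0.63. With 25 per arm the detectable difference is 0.81 SD, and t-test power at 0.63 SD is 59%. SAP 2a gives 0.70 SD for the planned size. That does not match the protocol and is a separate matter; it is used below only as a second reference value.

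**2. What a van Elteren p-value can show.** Simulation: 20,000 replicates, change scores with unit SD, a shift between arms, two strata. Type I error was about 5% throughout.

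| Shape of change | Power at 0.63 SD | Non-significant at 0.63 SD | Non-significant at 0.70 SD |
|---|---|---|---|
| Normal | 56% | 44% | 35% |
| Laplace (peaked) | 71% | 29% | 21% |
| t with 3 df (heavy tails) | 82% | 18% | 11% |

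So a non-significant result is compatible with a difference of the size in the hypothesis.

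**3. What an interval would add.** Half-width of the 95% CI, in SDs of the 6-hour value:
- change: t(47) × √(2/25) × √(2(1 − rho)) = 0.569 × √(2(1 − rho))
- baseline-adjusted: t(46) × √(2/25) × √(1 − rho²) = 0.569 × √(1 − rho²)

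| rho | Change | Adjusted | Ratio adjusted/change |
|---|---|---|---|
| 0.3 | 0.67 | 0.54 | 0.81 |
| 0.5 | 0.57 | 0.49 | 0.87 |
| 0.7 | 0.44 | 0.41 | 0.92 |
| 0.87 | 0.29 | 0.28 | 0.97 |
| 0.9 | 0.25 | 0.25 | 0.98 |

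Adjustment narrows the interval by about 19% at rho 0.3 and by about 3% at 0.87 to 0.9.

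**4. The scale matters.** Protocol 1 does not say which SD the 0.63 refers to. In SDs of change, the change half-width is 0.57 at every rho. The adjusted one is 0.569 × √((1 + rho)/2), which is 0.46 at rho 0.3 and 0.55 at rho 0.9. An estimate from the change analysis would therefore have to lie within about 0.63 − 0.57 = 0.06 SD of zero for the interval to exclude 0.63 SD. With normal data and no true difference, the whole interval falls inside ±0.63 SD of change in about 19% of trials for the change analysis. For the adjusted analysis the figure runs from 54% (rho 0.3) down to 23% (rho 0.9).

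**5. Is the regression interval usable with peaked data?** In simulations of 50 infants with Laplace and t (3 df) data, coverage of the ordinary 95% CI was 94.8% to 95.9%. Peakedness of that kind does not by itself rule it out.

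**The case against.** Much of the case for the SAP stands.

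- **The test is valid.** It holds its error rate and can be more powerful than regression with heavy tails: with t (3 df) data at rho 0.7, simulated power at 0.63 SD (of the 6-hour value) was 93% against 88%. A reader might infer that Wilcoxon was the wrong test; the documents and the figures do not support that.
- **Using change is not a departure.** Change is the defined outcome, and the protocol's own fallback also gives up baseline adjustment.
- **No planned interval was dropped.** Neither document plans one. The SAP calls van Elteren preferred and does not expressly delete the regression, so this is a gap in what is named.
- **Reasons are given.** SAP 6c cites a peaked distribution, most naturally that of the 6-hour change, and 10a cites non-normality. Neither says whether the regression requirements failed or why the t-test fallback was passed over. That is missing detail and does not carry the point.
- **Regression is not the protocol's first choice for the primary outcome overall.** That is the mixed model, unless losses are differential. Regression comes first only at individual time points, so a 6-hour regression cannot test every choice made after the data were seen.
- **If the regression requirements fail, the protocol points to the stratified t-test on change.** That also yields a mean difference and an interval, and the fix allows for it.
- **An interval may settle nothing** (step 4), and the study is declared exploratory (SAP 11). Exploratory status does not remove the need for an estimate: a small trial is informative mainly through an estimate with its uncertainty.

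**Conclusion.** The point holds as a reporting gap that is cheap to close. For 6-hour FiO2, SpO2 and respiratory rate, the SAP names a valid test but no treatment difference and no interval, although both of the protocol's analyses for a single time point would supply a difference. With about 50 infants, a non-significant p-value would leave a 0.63 SD difference (of change) open, with an 18% to 44% chance of that result if such a difference were real.

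A reader might treat 0.63 SD as an equivalence margin. The documents do not support that: it is the difference that 40 per arm could detect, and SAP 11 says the sample size was set by recruitment time and not by a pre-determined clinically significant difference. It serves only as a reference value.

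The sizes rest on the assumed split by arm and stratum, the 6-hour count of 50, the distribution shapes and the range of rho. The gain in precision from adjustment may be small. SAP 2b's warning that FiO2 is hard to interpret when SpO2 is above target limits any FiO2 estimate, whichever method produces it.

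**What to change.** In SAP 6c, and in 10a for SpO2 and respiratory rate only:

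1. Keep van Elteren.
2. Report beside it the between-arm difference at 6 hours with a 95% CI, from the protocol's regression of the 6-hour value on arm, stratum and baseline. A robust or bootstrap interval is acceptable.
3. If the regression requirements are judged to have failed, also report the protocol's stratified mean difference in change with its 95% CI.
4. Label these results as added after the data were seen, and give all of them whichever is more favourable.
5. Give estimates in raw units, and state which SD (of change or of the 6-hour value) is used in any comparison with 0.63 SD.
6. Add a sentence saying whether the regression requirements failed and why Wilcoxon replaced the stratified t-test.

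CPAP duration is outside this change because it has no baseline and van Elteren was already planned for it. So are the blood gases, where only five infants had both readings.

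The cost is a few lines of SAS on data already collected and a few sentences of text. The results may disagree, and that would need discussion.
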